16.4 Part 1 to Part 2 transition procedures

16.4.1 General approach

The MA1 (unblinded) will be performed after approximately 200 patients have completed Day 28, either as scheduled or prematurely, while enrollment continues.

Based on the MA1 results the trial may be expanded into Part 2, if activity of IMU-838 is observed, or stopped, if no activity of IMU-838 is observed. A further 30 patients are expected to be enrolled

and treated in a double-blind manner until the results of the MA1 are available (when no activity of IMU-838 was found) or until the enrollment in Part 2 has commenced (if MA1 indicated proof-of-activity). Criteria to assess activity of IMU-838 that will guide the decisions to expand the trial are based on efficacy, virology and biomarker endpoints and are defined in Section 16.4.2 below. The IDMC will also review MA1 results and act as a consultative capacity to assist the Sponsor in decision making, sample size calculations, endpoint selection and other adjustments for Part 2.

A final analysis of Part 1 (FA1) will be performed after completion of Part 1, pooling all enrolled patients, i.e. about 230 patients for any outcome evaluated in the MA1.

The sample size of Part 2 will be estimated based on the MA1 results. Possible other adjustments (e.g., modifications to endpoints, concomitant medications and to SoC, inclusion of children, and other adjustments) will be considered and discussed between the Sponsor and the IDMC. Part 2 will use an adaptive sequential trial design. An unblinded IA will be performed by the IDMC after approximately 50% of patients have been enrolled (based on the Part 2 sample size) to re-assess sample size based on available safety and efficacy data. The Part 2 of the trial will be designed to keep a global 1-sided alpha level of 0.025. A 2-stage group sequential test adaptive design with O'Brien and Fleming shaped boundaries will be used. The IA during Part 2 is assumed a Stage 1 analysis applying an overall information rate of 50% and using an alpha of 0.0026.

The use of group sequential boundaries within the context of an adaptive design is enabled by using the inverse normal method, combining the p-values of both stages with weights based on the sample sizes.

16.4.2 “Activity” criteria and further issues to be considered

The activity of IMU-838 will be evaluated based on the following endpoints:

- Proportion of patients without any need for INV until EoS (primary endpoint)

In all 3 scenarios, the assessed clinical endpoints, virologic data, and/or biomarker must show an overall general pattern that is consistent with IMU-838 having clinical activity in COVID-19 patients.

A robust trend of IMU-838 activity versus placebo must be observed. If none of the above criteria is met without any robust trend on efficacy endpoints of IMU-838 versus placebo, Part 2 will not be initiated, and enrollment of Part 1 will be stopped.

If clinical activity of IMU-838 is confirmed, the following will additionally be evaluated

- Re-evaluation of the primary and key secondary endpoints
- The sample size for Part 2 based on the MA1
 - Assumptions:
 - 2-stage group sequential test design with O'Brien and Fleming shaped boundaries
 - Information rate for IA2: 0.50
 - O'Brien and Fleming alpha level for IA2: 0.0026
 - Primary endpoint: Proportion of patients without any need for INV (if not changed after MA1)
 - Randomization ratio: 1:1 (45 mg/day IMU-838:placebo)
 - Power: 80%
 - Global significance level: 0.025, 1-sided
 - Proportions in primary endpoint as observed during MA1A drop-out rate as observed during MA1 will be considered
- Re-evaluation of inclusion and exclusion criteria
- Inclusion of children and adolescents 12 years or older
- Modifications on dose and/or treatment duration
- Modifications on allowed or prohibited concomitant medications and medications to be considered for standard of care
- Safety review
 - Any safety signal which require a change in trial conduct
 - Are additional safety analyses before the next IDMC meeting required?
- Are any other adjustments to the trial conduct (not previously covered) needed?
- Re-evaluation of the number of patients per country and center

If activity and safety of IMU-838 is confirmed, enrollment will be stopped, when Part 2 is initiated, and FA1 will be performed.

17 Patient stopping rules and other reasons for patient withdrawal from trial participation

17.1 Patient stopping rules

Any SAE of Grade 3 or 4, when in the investigator's opinion the benefits do not outweigh the risk for continuing in the trial.

17.2 Other reasons for patient withdrawal from trial participation

Participation in the trial is voluntary and patients may withdraw from the trial at any time and for any reason. However, all patients will be encouraged to complete the trial and have EoS assessment performed (Day 28) (also refer to Section 12).

Patients must be withdrawn from the trial for any of the following reasons:

- Patient withdraws consent due to
 - AE(s)
 - COVID-19 related clinical events
 - other reason (to be specified)
for all patient withdrawals it should be recorded whether the patient agrees to all non-interventional follow-up procedures
- Investigator decision due to
 - AE(s), which in the opinion of the investigator may jeopardize the patient's health or may compromise the trial objectives
 - relevant non-compliance with the protocol, which in the opinion of the investigator may jeopardize the trial integrity or scientific goals of the trial
 - reasons other than AE or non-compliance (to be specified)
- Lost to follow-up (including transfer of patient to a different medical institution inaccessible to the investigator)
- Death
 - Primarily related to COVID-19 and its complications
 - Not primarily related to COVID-19 and its complications
- Pregnancy
- Treatment with prohibited concomitant medication (see Section 11.2, [Prohibited and restricted medication](#))
- Violation of inclusion or exclusion criteria noted only after randomization

- The trial is terminated by the Sponsor

The primary reason for discontinuation from the trial is to be recorded in the source documents and on the early termination page of the eCRF.

If the patient withdraws consent, no further evaluations should be performed and no attempts should be made to collect additional data. However, the patient may allow to continue non-interventional follow-up procedures.

Patients who prematurely discontinue the trial will be treated according to the investigator's discretion and standard treatment guidelines, irrespective of the reason for withdrawal, and will not be replaced.

Reasonable efforts will be made to contact any patient lost to follow up, to complete assessments (including an EoS assessment) and to retrieve any outstanding data and IMP and supplies.

If the IMP will be prematurely discontinued, the primary reason for discontinuation is to be recorded in the appropriate section of the eCRF. Patients who discontinue therapy with IMP will be encouraged to continue with trial-related assessments (including EoS visit) until their trial completion.

18 Independent Data Monitoring Committee

An IDMC will be established including at least 3 members: an independent clinical virologist (or clinical infectious disease expert), an independent statistician, and an independent pharmacovigilance expert. The independent virologist will serve as Chair. However, additional independent experts may be added, as needed.

The IDMC will have access to efficacy and safety data and information regarding the quality of the data as outlined in the IDMC Charter.

The IDMC will have at least 4 planned formal meetings

- Inaugural meeting (at the start of the trial to discuss function and roles)
- Meeting for the early safety analysis
- Meeting for MA1
- Meeting for IA2, if applicable

More details on their responsibilities are outlined in Section [8.1](#).

If at the IA2 the IMU-838 therapy arm proves to be statistically significantly more beneficial, the patient enrollment will be stopped.

The IDMC may hold ad hoc teleconference meetings to discuss safety or trial conduct information as needed, or when new safety signals are observed in this trial or in other trials of IMU-838.

Further details on responsibilities and the working procedures of the IDMC will be specified in an IDMC charter.

19 Ethical and legal requirements

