The first dose of IMP (2 tablets) should always be given on Day 0 (allowed range for first dose: 12:00 noon on Day 0 to 02:00 a.m.). All further IMP doses are 1 tablet each in the morning and evening. For details of IMP administration see Section 11.1.5. Information about the status and patient care are continuously obtained and documented once or twice daily (see [Table 3](#)). Further examinations and tests, laboratory parameters, biomarkers, disease markers, and virologic parameters are to be assessed as outlined in [Table 3](#).

After the last IMP dose in the evening of Day 13, the end-of-treatment assessments will be done on Day 14 (see [Table 3](#)). Blood sampling for IMU-838 trough values must be performed in the morning around the time the morning dose was usually taken by the respective patient. Patients may then continue to receive SoC without any further restrictions on concomitant medications as during the 14-day BT period (see Section 11.2.1 and [IMP-related exclusion criteria](#)).

The assessments to be performed in case of hospital discharge before Day 14 are described in Section 12.3. *For centers in Bulgaria only: Patients must be hospitalized during the entire treatment period i.e., from Day 0 to Day 14.*

Day 28 Visit (EoS)

The patient should return for the final trial visit on Day 28 (EoS). If IMP is prematurely discontinued for any reason, the EoS visit should always be conducted on Day 28 and no earlier EoS should be performed. If patients withdraw from IMP prematurely, they should be encouraged to allow the EoS visit as part of the follow-up. If the patient dies during the trial, the investigator should indicate that this visit was not performed. However, even if no EoS visit was performed, information about patient status should be reported on the EoS page in the case report form. If the patient refuses any EoS visit or the patient is lost to follow-up, it is permissive in this trial that the investigator contacts the patient, the family of the patient or the referring physician by phone or email to obtain status of life information, or is able to search in registers or publicly available information for such status of life information.

Safety follow up

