11.2.2 Prohibited and restricted medication

The use of the following medications and treatments will be prohibited from Screening to end-of-treatment with IMP in this trial (up to Day 14) if not indicated otherwise in this protocol:

- Concurrent use of any mycophenolate mofetil or of methotrexate exceeding 17.5 mg weekly
- Any medication known to significantly increase urinary elimination of uric acid, in particular lesinurad (ZurampicTM) as well as uricosuric drugs such as probenecid
- Current treatments for any malignancy, in particular irinotecan, paclitaxel, tretinoin, bosutinib, sorafenib, enasidenib, erlotinib, regorafenib, pazopanib and nilotinib
- Any drug significantly restricting water diuresis, in particular vasopressin and vasopressin analogs
- Use of rosuvastatin at daily doses higher than 10 mg
- Arbidol and Colchicine
- Any use of other DHODH inhibitors, including teriflunomide (AubagioTM) or leflunomide (AravaTM)
- Chloroquine and Hydroxychloroquine are not allowed during the entire trial, unless already taken for indicated use before entering the trial

Routine use of steroids is not recommended and should be reserved for patients with severe disease or with special circumstances. Concomitantly used steroids (e.g., required for pre-existing conditions) do not need to be discontinued when entering this trial, however, their use should be carefully considered.

After the 14-day treatment period with IMP any drugs to treat the disease, including any anti-viral therapy, can be used at the investigator's discretion.

The concomitant administration of drugs metabolized for more than 70% by CYP2C8 (although not prohibited) should be carefully considered since it cannot be excluded that IMU-838 potentially increases their blood levels. Major substrates of CYP2C8 include:

- amodiaquine (anti-malarial)
- dasabuvir (anti-viral),
- enzalutamide (anti-cancer)
- montelukast (anti-asthmatic), and
- pioglitazone and repaglinide (anti-diabetics)

The use of the potent CYP2C8 inhibitor rifampicin and strong and moderate CYP2C8 inducers gemfibrozil and trimethoprim as concomitant medication is not prohibited during this trial. However, alternatives to these drugs should be considered, and patients should be carefully monitored for any indication of toxicity. Given the known narrow therapeutic window of ibuprofen, the use of ibuprofen should be carefully considered or, if possible, therapeutic alternatives should be used.

12 Trial schedule

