16.3.2 Primary and key secondary efficacy endpoint analyses

In the following the analyses for the primary and key-secondary endpoints are described for Part 1. Since Part 1 and Part 2 will be independent parts, these endpoints may be changed for Part 2 after the MA1 analysis. More details and/or changes for evaluation in Part 2 will be specified in a protocol amendment and respective SAP when MA1 results are available.

Primary endpoint

The primary endpoint of the trial i.e., the proportion of patients without any need for INV until EoS. The “need for INV” (considered positive for the primary endpoint) will include patients:

1. placed on any INV method during the trial
2. who had an active “do not intubate” or “do not resuscitate” order established during the trial conduct or refused intubation for any reason but were assessed by the investigator to have a medical need for INV
3. who had a medical need for INV as assessed by the investigator but for reasons of medical resource exhaustion or due to triage decisions by the hospital had not received INV, or
4. who died mainly due to respiratory failure but had a need for INV as assessed by the investigator or before such needed INV could have been started

Patients who are lost to follow-up or discontinue the trial on or before Day 13 (last treatment day) due to any reason other than death and discontinue with a last observed WHO clinical status no lower than that at Screening, and patients who die and do not fall under Number 4 of the above-mentioned criteria will be considered treatment failures for the primary endpoint. A sensitivity analysis will be performed for patients who discontinued before EoS, using the available information on INV.

Invasive ventilation involves any instrument penetrating via the mouth (e.g., endotracheal tube), nose, or the skin (e.g., tracheostomy tube through a stoma) to serve as an artificial airway, and the manual or mechanical ventilation of the patient through such artificial airway.

For clarification, bilevel positive airway pressure (trademarked as BiPAP™ or VPAP™ by different manufacturers) and continuous positive airway pressure are not considered INV as they do not involve intubation. However, for classification of patient clinical status these methods are considered non-invasive ventilation (WHO Status 5, [Table 4](#)).

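### Mandatory trial withdrawal (17.2), with a failure rule keyed to discontinuation (16.3.2), lets an imputed failure displace a recorded Day 28 outcome in the FAS analysis

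*Combined protocol and SAP*

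**What the plan says.** **Withdrawal.** Section 17.2 introduces its list with "Patients must be withdrawn from the trial for any of the following reasons". Two entries matter here: "Treatment with prohibited concomitant medication" and "Violation of inclusion or exclusion criteria noted only after randomization". Both lead to withdrawal from the trial. Stopping IMP alone is dealt with separately at the end of 17.2, where follow-up continues.

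**Follow-up.** The opening of 17.2 also says: "However, all patients will be encouraged to complete the trial and have EoS assessment performed (Day 28"). Section 12.5 asks for the end-of-study assessments at Day 28 after premature discontinuation whenever possible, and for survival status if the visit is refused or the patient is lost. The only bar on further data collection in 17.2 applies to withdrawn consent, and even then the patient may allow non-interventional follow-up.

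**Analysis.** In 16.3.2, primary-endpoint failure covers patients "lost to follow-up or discontinue the trial on or before Day 13 (last treatment day) due to any reason other than death" who also have a last WHO status no lower than at Screening. A sensitivity analysis uses the INV information available. Section 16.2 describes the FAS analysis as intention-to-treat.

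**Timing.** Section 11.2.2 says the listed drugs "will be prohibited from Screening to end-of-treatment with IMP in this trial (up to Day 14"), with chloroquine and hydroxychloroquine barred for the whole trial outside prior indicated use. Most withdrawals for prohibited medication would therefore fall inside or next to the Day 13 window.

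**The concern.** A protocol deviation or a late-found eligibility error is a reason to record a deviation and perhaps to exclude the patient from the per-protocol set. It is not an outcome. Here it becomes one, because the failure rule looks at whether and when the patient left the trial, not at whether the Day 28 outcome is missing. A patient withdrawn on Day 8 for a prohibited drug, unimproved at that time and later documented as never needing INV, is a failure in the main analysis.

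The withdrawn patients need not be a random sample. Extra drugs may go to patients who are not improving, and the WHO-status condition picks out those patients. Part 1 has no formal test, so type I error is not at stake. What is at stake is the estimated effect, the activity decision at the main analysis of Part 1 (MA1, Section 16.4.2) and the Part 2 sample size, which takes its proportions from MA1.

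**Working it through.** **1. Which patients are imputed, and when**

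- Primary endpoint, 16.3.2: both conditions are needed, namely trial discontinuation by Day 13 and WHO status no lower than at Screening. Patients who had improved, or who were withdrawn later, are not imputed.
- Synopsis (all these endpoints) and 16.3.2 for respiratory failure and ICU duration: the second condition is attached to a separate group of patients, so either condition alone suffices. An improved patient withdrawn by Day 13 would then also be imputed.
- ICU duration, 16.3.2: with no known ICU stay, ICU time is imputed from discontinuation to Day 28. Withdrawal on Day 7, for example, gives 28 − 7 = 21 days. With a known stay, its end is set to Day 28.
- Mortality, 16.3.2: discontinuation before Day 28 counts as death only if survival status cannot be obtained. A recorded survival status is not overridden.

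**2. The plan's own figures (Section 16.1)**

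Inputs: need for INV 32% (IMU-838) and 40% (placebo), 1-sided alpha 0.05, power 80%, 1:1 allocation, information rate 0.2, drop-out 6%. The continuity-corrected two-proportion formula gives 469 per arm, or 938 in total. Then 938 × 0.2 = 187.6, i.e. 188, and 188 / 0.94 = 200. Both stated figures are reproduced.

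**3. Effect of imputing a share w of an arm as failures**

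The documents give no w for these two reasons. I assume 0 to 6 per 100, the upper end being the whole all-cause drop-out. I also assume that every such patient meets the failure rule and would otherwise have had the planned risk p. The need rate becomes p(1 − w) + w.

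For w = 6% in both arms:

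- IMU-838: 0.32 × 0.94 + 0.06 = 0.3608
- Placebo: 0.40 × 0.94 + 0.06 = 0.4360
- Relative reduction in need: (0.4360 − 0.3608) / 0.4360 = 17.2%
- Relative gain in success: 0.6392 / 0.5640 − 1 = 13.3%

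| Imputed share, IMU-838 / placebo | Need for INV, IMU-838 vs placebo | Relative reduction in need | Relative gain in success |
|---|---|---|---|
| 0% / 0% | 32.0% vs 40.0% | 20.0% | 13.3% |
| 3% / 3% | 34.0% vs 41.8% | 18.6% | 13.3% |
| 6% / 6% | 36.1% vs 43.6% | 17.2% | 13.3% |
| 6% / 0% | 36.1% vs 40.0% | 9.8% | 6.5% |
| 0% / 6%, no true effect | 40.0% vs 43.6% | 8.3% | 6.4% |

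If only half of a 6% group meets the WHO condition, the 3% row applies.

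The number of outcomes actually changed is smaller than w, because some of these patients would have needed INV anyway. At 6% it is 6 × 0.68 = 4.1 per 100 on IMU-838 and 6 × 0.60 = 3.6 per 100 on placebo. If withdrawn patients are at higher risk than average, fewer still are changed.

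**4. Consequence for Part 2**

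Fixed design, 1-sided alpha 0.025, power 80%, no continuity correction: 564 per arm at 32% vs 40%, 613 at w = 3% in both arms, and 665 at w = 6% (665 / 564 = 1.18, i.e. 18% more).

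**The case against.** The strongest reply is that the protocol already seeks the data and limits the damage. Several stronger readings that a reader might infer do fail on the documents.

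- **That 17.2 removes Day 28 outcomes.** It does not. Section 17.2 and Section 12.5 still seek the assessment, and 17.2 asks for a record, at every withdrawal, of whether the patient agrees to non-interventional follow-up.
- **That 17.2 flatly contradicts Section 8.1.** The sentence there, "If IMP is prematurely discontinued for any reason, the EoS visit should always be conducted on Day 28", governs stopping IMP, which is a different event from leaving the trial. The tension lies within 17.2 and between 17.2 and 12.5.
- **That withdrawn patients are counted as deaths.** This happens only where survival status cannot be traced, and a sensitivity analysis makes the opposite assumption.
- **That patients in shock are withdrawn for receiving vasopressin.** Section 11.2.2 does list "Any drug significantly restricting water diuresis, in particular vasopressin and vasopressin analogs", but it does not bar vasopressors as a class, and 11.2.1 counts vasopressor support as standard care. On the WHO scale, pressors appear together with ventilation, so such a patient would usually be an observed INV failure already.
- **That six imputed patients per 100 nearly cancel an 8-point effect.** This sets an all-cause count within one arm against a difference between arms. Equal imputation at 6% reduces the absolute difference only from 8.0 to 7.5 points.

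It is also fair that sensitivity analyses on available data exist for INV, respiratory failure and ICU duration. They would show the discrepancy. They do not change which analysis is primary, and the trigger in 16.3.2 remains discontinuation and not missingness. That part of the concern stands.

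**Conclusion.** The point holds. Section 17.2 requires trial withdrawal for two reasons that are not outcomes, in tension with its own opening and with 12.5. Section 16.3.2 can then replace a recorded outcome with a failure in an analysis described as intention-to-treat.

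The size is modest if the arms are affected equally: at most a fall from 20% to 17.2% in the relative reduction in need for INV, and no change on the success scale. It matters more if the arms differ. With 6% on IMU-838 only, a true 20% appears as 9.8%, just under the 10% tier in 16.4.2. With 6% on placebo only, a null effect appears as 8.3%, above the 5% component of the third tier, although that tier also requires secondary and virologic effects.

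These are upper-range illustrations. They rest on an assumed share of 0 to 6 per 100, on all such patients meeting the failure rule, and on planned risks otherwise. The unequal cases are assumptions; nothing in the documents predicts an imbalance.

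**What to change.** Reconcile the list in 17.2 with the opening of 17.2 and with 12.5, and amend 16.3.2 and the synopsis:

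1. State that patients withdrawn for prohibited medication or for eligibility violations found after randomization remain in data collection to Day 28 unless they withdraw consent.
2. State that in the FAS analysis of the primary and key secondary endpoints an observed outcome takes precedence, and that imputation is used only when the outcome is actually missing.
3. Use one wording of the imputation conditions in the synopsis and in the primary, respiratory-failure and ICU texts of 16.3.2, making clear whether both conditions are needed or either suffices.

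Leave decisions about IMP, the pregnancy rule in 15.1.8 and termination by the sponsor to the existing text. The cost is wording only, since the Day 28 visit and survival tracing are already in the protocol. The change should be in place before the data for MA1 are unblinded.
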